	
A minimum of 30 male or female pediatric patients will be enrolled in this study with 3 patients in each low-dose group for age cohorts 1, 2, 3 and 4; and 6 patients in each high-dose group for age cohorts 3 and 4, and 3 (maximum 6) patients in each high-dose group for age cohorts 1 and 2. The four age cohorts are as follows:
 
• Cohort 1: 6 to <18 years [3 low-dose patients, 3 high-dose patients (maximum 6)]• Cohort 2: 1 to <6 years [3 low-dose patients, 3 high-dose patients (maximum 6)]• Cohort 3: infants 1 month to <1 year [3 low-dose patients, 6 high-dose patients]• Cohort 4: neonates birth to <1 month [3 low-dose patients, 6 high-dose patients] 
Age cohorts will be enrolled sequentially from age cohort 1 to 4, within each dose group. For each age cohort, patients will be enrolled first into the low-dose group and if it is considered safe after a review of all available safety and pharmacokinetic (PK) data, up to and including study day 5, then patients will be enrolled into the low-dose group for the succeeding age cohort. Patients cannot be enrolled into the high-dose group for a given age cohort until data from the low-dose group of that same age cohort and the high-dose group of the preceding age cohort (where present) has been reviewed and it is considered safe to proceed.

Population	
The study population will consist of 30 male or female pediatric patients (birth to <18 years of age) hospitalized with the following: signs and symptoms of AHF who have a requirement for a stable dose of vasoactive and/or inotropic agents and, in patients with medical etiologies of AHF, echocardiographic evidence of reduced ventricular function.
 
Both, medical and post-surgical [REDACTED] [REDACTED] etiologicals of AHF can be included in the study. [REDACTED] [REDACTED]

Key Inclusion criteria (see protocol for full details)	
1. Male or female, [REDACTED], with body weight ≥ 2.5 kg to ≤ 120 kg2. Hospitalized in an intensive/critical care unit or continuously monitored step-down unit with the following:
a. signs and symptoms of AHF of any etiology andb. a stable dose of vasoactive and/or inotropic agents [REDACTED] [REDACTED]c. [REDACTED] [REDACTED] [REDACTED] [REDACTED] [REDACTED]

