[REDACTED] A total duration of 48 hours is planned for the constant iv serelaxin infusion with dose escalations every 16 hours. A low-dose group and a high-dose group will be enrolled sequentially in every age cohort. During this 48-hour treatment period, the serelaxin dose rates to be administered are 3 $\mu\text{g}/\text{kg}/\text{day}$, 10 $\mu\text{g}/\text{kg}/\text{day}$ and 30 $\mu\text{g}/\text{kg}/\text{day}$ in the low-dose group; 10 $\mu\text{g}/\text{kg}/\text{day}$, 30 $\mu\text{g}/\text{kg}/\text{day}$ and 100 $\mu\text{g}/\text{kg}/\text{day}$ in the high-dose group [REDACTED]. These dose rates are anticipated to be safe in the pediatric population and are based on the dose range investigated in adults with AHF.

Thirty (30) male or female pediatric patients (minimum) will be enrolled in this study with 3 patients in each low dose group for age cohorts 1, 2, 3 and 4; and 6 patients in each high-dose group for age cohorts 3 and 4, and 3 (maximum 6) patients in each high dose group for age cohorts 1 and 2. The four age cohorts are as follows:

- Cohort 1: 6 to <18 years [3 low-dose patients, 3 high-dose patients (maximum 6)]
- Cohort 2: 1 to <6 years [3 low-dose patients, 3 high-dose patients (maximum 6)]
- Cohort 3: infants 1 month* to <1 year [3 low-dose patients, 6 high-dose patients]
- Cohort 4: neonates birth to <1 month* [3 low-dose patients, 6 high-dose patients]

*1 month = 30 days

[REDACTED]

[REDACTED]

[REDACTED]

Age cohorts will be enrolled sequentially from age cohort 1 to 4, within each dose group. For each age cohort, patients will be enrolled first into the low-dose group and if it is considered safe after a review of all available safety and pharmacokinetic (PK) data, up to and including study day 5, then patients will be enrolled into the low-dose group for the succeeding age cohort. Patients cannot be enrolled into the high-dose group for a given age cohort until data from the low-dose group of that same age cohort and the high-dose group of the preceding age cohort (where present) has been reviewed and it is considered safe to proceed.

[REDACTED]

Enrollment within each dose group will be temporarily stopped 4 times for the low dose group and 3 times for the high dose group during the study for a review of safety and PK data as follows:

Low Dose Group

- 1st enrollment stop for low-dose, safety and PK data review after completion (up to day 5) of 3 low-dose patients in age cohort 1

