- 2nd enrollment stop for low-dose, safety and PK data review after completion (up to day 5) of 3 low-dose patients in age cohort 2
- 3rd enrollment stop for low-dose, safety and PK data review after completion (up to day 5) of 3 low-dose patients in age cohort 3
- 4th enrollment stop for low-dose, safety and PK data review after completion (up to day 5) of 3 low-dose patients in age cohort 4.

High Dose Group

[figure not shown]
- 1st enrollment stop for high-dose safety and PK data review after completion (up to day 5) of 3 high-dose patients in age cohort 1
- 2nd enrollment stop for high-dose, safety and PK data review after completion (up to day 5) of 3 high-dose patients in age cohort 2
- 3rd enrollment stop for high-dose, safety and PK data review after completion (up to day 5) of 6 high-dose patients in age cohort 3

[figure not shown]
Note: For a given age cohort, high-dose patients can only be enrolled after 3 low-dose patients have been enrolled in that age cohort and 3 patients have been enrolled in the high-dose group of the preceding age cohort (as applicable), and their safety and PK data reviewed, and it is considered safe to proceed. For any additional high-dose group, age cohort 1 or 2 patients (i.e. beyond the 3 required patients), their data will be reviewed at the next available PSRC meeting.

[REDACTED]

[REDACTED]

[REDACTED]

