3.6 Risks and benefits

In adults, hospitalization and worsening heart failure with accompanying end organ damage, such as worsening renal function and myocardial injury, are both associated with increased mortality. In two adult AHF studies (pre-RELAX-AHF, [Teerlink et al, 2009](#) and RELAX-AHF, [Teerlink et al, 2013](#)) a 48 hour serelaxin infusion on top of SOC led to a significant relieve of dyspnea and congestion, the presenting elements of AHF in adults, compared to placebo on top of SOC. This was associated with a significant reduction in early worsening of HF (defined as intensification of HF therapy) and length of (index) hospitalization and intensive care unit stay

[REDACTED]

Overall, serelaxin (on top of SOC) was well-tolerated with an adverse event profile comparable to placebo (on top of SOC). Although slightly more hypotension-related adverse events were reported in the serelaxin treatment arm versus placebo due to its vasodilatory effects, without a dose-response or exposure-response relationship, the use of stringent blood pressure inclusion criteria and the management of blood pressure decreases during serelaxin

[REDACTED]

infusion (i.e. mandated 50% dose reduction and/or discontinuation if pre-specified blood pressure decreases were met) have demonstrated that serelaxin-induced hypotensive effects were generally mild and easily manageable without causing harm and the majority of patients were able to stay on drug.

several safeguards are included in the CRLX030A2208 study design in order to reduce the risk in this new patient population as much as possible. First, a low-dose group, dosed at 3, 10 and 30 μ g/kg/day (within-patient dose escalation every 16 hours) will be enrolled ahead of every high-dose group, which is dosed at 10, 30 and 100 μ g/kg/day (also within-patient dose escalation every 16 hours). The high-dose group will only be enrolled if the review of safety and PK data (up to day 5) from the low-dose group shows that it is safe to do so. Second, age cohorts will be enrolled sequentially and younger age cohorts will only be allowed into the study once the review of safety and PK data (up to day 5) from the preceding older age cohort shows that it is safe to do so. Third, the risk to the patient will also be minimized by compliance with the inclusion/exclusion criteria that aim to recruit patients with mild to moderate hemodynamic impairment, excluding the sickest and most vulnerable individuals in this population.

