8.4 Interim safety and PK data review

As described in [Section 3.1](#), Study design, [REDACTED]

[REDACTED], age cohorts will be enrolled sequentially, within each dose group, from age cohort 1 to 4. For each age cohort, 3 patients will be enrolled first into the low-dose group and if it is considered safe after review of all available safety and PK data (up to and including study day 5), then patients will be enrolled into the low-dose group for the succeeding age cohort. No patients will be enrolled into the high-dose group for a given age cohort until data from the low-dose group of that same age cohort and the high-dose group of the preceding age cohort is reviewed and it is considered safe to proceed. Data review is anticipated to include the following, when available:

- AEs and SAEs and their causal relationship to the study drug
- Hypotension events, dose adjustments and discontinuations
- Evidence of pharmacodynamic interactions between serelaxin and co-medications
- Vital signs, respiratory parameters and clinical assessments
- Blood chemistry, hematology, blood gas and serum lactate levels, and renal biomarkers (as available)
- PK

[REDACTED]

[REDACTED]

[REDACTED]

[REDACTED]

[REDACTED]

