9.7 Sample size calculation

Sample size is guided by feasibility in pediatric patient studies for assessment of safety, tolerability and pharmacokinetics.

The sample size planned for the high-dose group (10/30/100 µg/kg/day) per age cohort will be 6 subjects. With a sample size of 6 subjects per age cohort, receiving RLX030 at various doses, there is ~80% probability to observe an adverse event with an underlying occurrence rate of 24% at least once for each cohort and dose combination during the study. With a sample size of 3 subjects per age cohort, receiving RLX030 at various doses, there is ~56% probability to observe an adverse event with an underlying occurrence rate of 24% at least once for each cohort and dose combination during the study.

Data from 6 subjects will also provide ~80% probability for the 95% confidence intervals (CI) of geometric means of RLX030 Css to fall within the range of (68%U, 146%U), data from 3 subjects will provide ~80% probability for the 95% confidence intervals (CI) of geometric means of RLX030 Css to fall within the range of (39%U, 257%U), where U is the observed geometric mean, assuming a coefficient of variation of 30% [REDACTED]

[REDACTED] an additional 3 subjects will be enrolled into a low-dose group (3/10/30 µg/kg/day) in each age cohort. The purpose of this low-dose group is to further enhance the safety by collecting safety data at a starting dose of 3 µg/kg/day up to the adult efficacious dose of 30 µg/kg/day, before enrolling patients in the high-dose group.

These calculations were performed using nQuery.

10 Ethical considerations

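### Protocol Section 3.1 gives two counts, 3 and 6, for the infant high-dose patients to be reviewed before neonatal high-dose enrollment opens

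*Protocol*

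**What the plan says.** Protocol Section 3.1 schedules three pauses in high-dose enrollment. The first two come after 3 completed high-dose patients in cohorts 1 and 2. The last is the "3rd enrollment stop for high-dose, safety and PK data review after completion (up to day 5) of 6 high-dose patients in age cohort 3".

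The Note directly below applies to any given cohort. It makes high-dose enrollment conditional on 3 low-dose patients in the same cohort, and on "3 patients have been enrolled in the high-dose group of the preceding age cohort (as applicable), and their safety and PK data reviewed". The Note's next sentence deals with extra patients and names two cohorts only: "For any additional high-dose group, age cohort 1 or 2 patients (i.e. beyond the 3 required patients".

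The same section also states the order of enrollment: "Age cohorts will be enrolled sequentially from age cohort 1 to 4, within each dose group".

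Elsewhere the gate appears without a number. The synopsis and the main text of Section 3.1 require that data from "the high-dose group of the preceding age cohort (where present) has been reviewed and it is considered safe to proceed". Section 8.4 says much the same: "the high-dose group of the preceding age cohort is reviewed and it is considered safe to proceed". Section 9.6 of the protocol and Section 12 of the SAP refer back to Section 3.1 for design details.

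**The concern.** The step into neonates is the last high-dose gate in the trial and the only one where the Note and the stop list disagree. Section 3.6 names sequential review as a safeguard for younger patients: "younger age cohorts will only be allowed into the study once the review of safety and PK data (up to day 5", and so on. It gives no count, so it cannot settle the matter.

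A committee or site team working from the Note could treat 3 reviewed infants as enough. One working from the stop list would wait for 6. A dose-escalation plan should not leave that threshold to interpretation, because the data reviewed at this gate are the infant high-dose safety and PK results. The effect of age on PK is also a primary objective.

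**Working it through.** **1. The two texts, gate by gate.** Counts are high-dose patients in the preceding cohort, from Protocol Section 3.1.

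| High-dose cohort to open | Preceding cohort | Stop list | Note |
|---|---|---|---|
| 2 (1 to <6 years) | 1 | 3 | 3 |
| 3 (1 month to <1 year) | 2 | 3 | 3 |
| 4 (birth to <1 month) | 3 | 6 | 3 |

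The low-dose counts agree throughout (3 per cohort). The mismatch is confined to the last row.

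**2. Reproducing the plan's figures (Protocol Section 9.7).** The inputs are an event rate of 24%, a coefficient of variation of 30%, and n = 3 or 6.

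- P(at least one event) = 1 − 0.76^n. For n = 3 this is 1 − 0.439 = 0.561, which matches the statement that "there is ~56% probability to observe an adverse event with an underlying occurrence rate of 24% at least once". For n = 6 it is 1 − 0.193 = 0.807, matching the stated ~80%.
- Css range = exp(± t(0.975, n−1) × s × √(χ²(0.80, n−1)/(n−1)) / √n), with log-scale SD s = 0.30. For n = 6 this gives (68.4%, 146.2%), and for n = 3 it gives (38.9%, 257.4%). Both match the stated (68%U, 146%U) and (39%U, 257%U).
- Minimum total = 4×3 + 3 + 3 + 6 + 6 = 30, as stated.

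No sample-size figure is wrong.

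**3. What the count changes among infant high-dose patients.**

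| Quantity | 3 reviewed | 6 reviewed |
|---|---|---|
| P(no event) at 24% | 0.76³ = 43.9% | 0.76⁶ = 19.3% |
| Event rate seen at least once with 80% probability, 1 − 0.20^(1/n) | 41.5% | 23.5% |
| One-sided 95% upper bound after zero events, 1 − 0.05^(1/n) | 63.2% | 39.3% |
| Css range (Section 9.7) | (39%U, 257%U) | (68%U, 146%U) |

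The 24% is a planning value. At a true rate of 10%, the chance of at least one event is 27% against 47%. At 40% it is 78% against 95%.

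**4. What it changes across the whole trial.** High-dose patients reviewed before the neonatal gate:

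- At cohort minimums: 3+3+3 = 9 against 3+3+6 = 12.
- With cohorts 1 and 2 filled to 6: 6+6+3 = 15 against 6+6+6 = 18.
- Adding the 4×3 = 12 low-dose patients gives totals of 21 against 24, or 27 against 30.

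At minimums, P(no event) among all high-dose patients is 0.76⁹ = 8.5% against 0.76¹² = 3.7%, assuming the same rate at every age.

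**5. Could a review of 3 infants arise in practice?** Under Section 3.1, low-dose cohort 4 opens after review of low-dose cohort 3. High-dose cohort 3 opens after that same review plus review of high-dose cohort 2. Low-dose cohort 4 and high-dose cohort 3 can therefore enroll in parallel. The fourth low-dose stop, with its review, could fall when only 3 to 5 high-dose infants have completed day 5. If the committee looked at those infants' data then, the Note's literal condition would be met before the third high-dose stop.

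**The case against.** The strongest reply is that the texts do not conflict. The Note states a necessary condition, the stop list schedules the actual review, and waiting for 6 satisfies both. The context also points to 6:

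- Section 3.1 allows exactly three high-dose stops, and none falls at 3 patients in cohort 3.
- Cohorts enroll in sequence within a dose group.
- The high-dose size for cohort 3 is fixed at 6, whereas cohorts 1 and 2 need 3 with a maximum of 6.
- The Note's sentence on patients beyond the required 3 names only cohorts 1 and 2, which suggests that its 3 was written with those cohorts in mind.

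The gate also needs reviewed data and a judgement that it is safe to proceed. Interim reviews belong to the PSRC, so a site is unlikely to open a cohort on a count alone. Finally, Section 3.5 and parts of Sections 3.1 and 8.4 are redacted, and a reconciling sentence may sit there.

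Most of this stands. It makes 6 the more natural reading and limits the practical risk mainly to the committee's own decision. It does not remove the mismatch. Among the visible text, only the Note attaches a number to the condition for opening the next high-dose cohort, and it makes no exception for cohort 4. Its qualifier about applicability fits cohort 1, which has no preceding cohort. The reading of 6 has to be inferred, and step 5 of the working shows how the literal condition could be met earlier.

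**Conclusion.** The concern holds and should be fixed. On the visible text, Section 3.1 carries two counts, 3 and 6, for the infant high-dose patients reviewed before neonatal high-dose enrollment, with no rule of precedence.

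The gap is 3 patients. For infant-specific data it is large: a 44% against a 19% chance of seeing no event at the 24% planning rate, and a much wider Css interval. For the pooled high-dose experience it is modest, at 8.5% against 3.7%. These figures assume independent patients, and the pooled ones also assume a common event rate across ages.

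The conclusion does not say which count is right. It concerns the plan as written: the SAP Introduction reports that the study ended early, and nothing here bears on what was done.

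**What to change.** Reconcile the Note with the third high-dose stop, so that Section 3.1 states one number of cohort 3 high-dose patients who must have completed day 5 and been reviewed before cohort 4 high-dose opens. The simplest route is for the Note to refer to the stop list instead of repeating a count. The Note also speaks of patients enrolled and reviewed, while the stop list speaks of patients completed to day 5, so the same edit should align that wording. Section 8.4 and the synopsis should then agree with it.

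The sponsor and the safety review committee should choose the number. The cost is protocol wording only, with a possible short delay to cohort 4 depending on the choice.

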3.2 Rationale of study design

This first open-label study in pediatric patients from birth to <18 years, hospitalized with AHF, is designed to evaluate the safety, tolerability and pharmacokinetics of escalating doses of serelaxin.

Qualifying study participants will receive serelaxin during the hospitalization in addition to SOC therapy for AHF according to local guidelines or institutional standards.

3.3 Rationale of dose/regimen, route of administration and duration of treatment

[REDACTED]

3.4 Rationale for choice of comparator

Not applicable

3.5 Purpose and timing of interim analyses/design adaptations

[REDACTED]

3.6 Risks and benefits

In adults, hospitalization and worsening heart failure with accompanying end organ damage, such as worsening renal function and myocardial injury, are both associated with increased mortality. In two adult AHF studies (pre-RELAX-AHF, [Teerlink et al, 2009](#) and RELAX-AHF, [Teerlink et al, 2013](#)) a 48 hour serelaxin infusion on top of SOC led to a significant relieve of dyspnea and congestion, the presenting elements of AHF in adults, compared to placebo on top of SOC. This was associated with a significant reduction in early worsening of HF (defined as intensification of HF therapy) and length of (index) hospitalization and intensive care unit stay

[REDACTED]

Overall, serelaxin (on top of SOC) was well-tolerated with an adverse event profile comparable to placebo (on top of SOC). Although slightly more hypotension-related adverse events were reported in the serelaxin treatment arm versus placebo due to its vasodilatory effects, without a dose-response or exposure-response relationship, the use of stringent blood pressure inclusion criteria and the management of blood pressure decreases during serelaxin

[REDACTED]

infusion (i.e. mandated 50% dose reduction and/or discontinuation if pre-specified blood pressure decreases were met) have demonstrated that serelaxin-induced hypotensive effects were generally mild and easily manageable without causing harm and the majority of patients were able to stay on drug.

several safeguards are included in the CRLX030A2208 study design in order to reduce the risk in this new patient population as much as possible. First, a low-dose group, dosed at 3, 10 and 30 μ g/kg/day (within-patient dose escalation every 16 hours) will be enrolled ahead of every high-dose group, which is dosed at 10, 30 and 100 μ g/kg/day (also within-patient dose escalation every 16 hours). The high-dose group will only be enrolled if the review of safety and PK data (up to day 5) from the low-dose group shows that it is safe to do so. Second, age cohorts will be enrolled sequentially and younger age cohorts will only be allowed into the study once the review of safety and PK data (up to day 5) from the preceding older age cohort shows that it is safe to do so. Third, the risk to the patient will also be minimized by compliance with the inclusion/exclusion criteria that aim to recruit patients with mild to moderate hemodynamic impairment, excluding the sickest and most vulnerable individuals in this population.

Female patients of child bearing potential should be informed that taking the study drug may involve unknown risks to the fetus, if pregnancy were to occur during the study. Informed consent (and assent where required) that outlines the risks as well as protocol specific safety rules to adhere to the contraception requirements for the duration of the study has to be signed. In the case of any concerns regarding compliance with these requirements the patient should be excluded or discontinued from the study. In addition, females of child bearing potential

[REDACTED] are required to have a negative serum pregnancy test before entering the study.

Refer to the IB for additional information regarding the safety profile of serelaxin.

[REDACTED]

4 Population

The study population will consist of a minimum of 30 male or female pediatric patients (birth to <18 years of age) hospitalized with the following: signs and symptoms of AHF who have a requirement for a stable dose of vasoactive and/or inotropic agents and, in patients with medical etiologies of AHF, echocardiographic evidence of reduced ventricular function. Both, medical and post-surgical

[REDACTED]

etiologicals of AHF can be included in the study.

[REDACTED]

4.1 Inclusion criteria

Patients eligible for inclusion in this study have to fulfill all of the following criteria:

1. Written informed consent by parent(s)/legal guardian(s) for the pediatric patient must be obtained before any study-specific assessment is performed. A consent or assent may also be required for some patients depending upon their age and local requirements
2. Male or female, [REDACTED], with body weight ≥ 2.5 kg to ≤ 120 kg (basis for inclusion criteria weight: pre-operative weight for post-operative patients and weight on hospital admission for non-surgical patients)
3. Hospitalized in an intensive/critical care unit or continuously monitored step-down unit with the following:
 - a) signs and symptoms of AHF of any etiology [REDACTED] and
 - b) a stable dose of vasoactive and/or inotropic agents [REDACTED]
 - c) [REDACTED]

[REDACTED]

Figure 1 consists of three vertically stacked bar charts. The top chart shows the percentage of patients with solid tumors (0.0-100.0%) across age groups (18-44, 45-64, 65+). The middle chart shows the percentage of patients with lymphoma (0.0-100.0%) across the same age groups. The bottom chart shows the percentage of patients with leukaemia (0.0-100.0%) across the same age groups. The x-axis for all charts is 'Age group' and the y-axis is 'Percentage'.

Age group	Solid tumor (%)	Lymphoma (%)	Leukaemia (%)
18-44	~10	~10	~10
45-64	~40	~30	~20
65+	~80	~50	~30

1. **What is the primary purpose of the proposed legislation?**

11. **What is the primary purpose of the *Journal of Clinical Endocrinology and Metabolism*?**

10.1007/s00332-010-9000-0

1 | Page

A large black rectangular redaction box covers the bottom portion of the page content, starting below the table and ending near the bottom of the page. It is positioned above a thin horizontal line.

10. *Journal of the American Statistical Association*, 1980, 75, 338-342.

— [REDACTED]

4. Systolic blood pressure (SBP) consistently equal to or greater than the calculated 25th percentile SBP for age and gender per [Appendix 3](#). [REDACTED]

[REDACTED]

[REDACTED]

[REDACTED]

5. Stable pulmonary function, i.e. patient is extubated or is stable on ventilator support.

[REDACTED]

[REDACTED]

[REDACTED]

